7.2. Ibrutinib and Placebo Administration

The sponsor will provide both ibrutinib and matching placebo. Study participants will be dispensed ibrutinib daily (ARM A) and matching capsule placebo (ARM B) through the investigational pharmacy at OSU. The matching placebo will be identical in size and shape, but do not contain ibrutinib.

Ibrutinib or placebo will be administered as capsules (3x140mg capsules) orally once daily with water. The capsules are to be taken around the same time each day with 8 ounces (approximately 240 mL) of water. The capsules should be swallowed intact and should not

be crushed and patients should not attempt to open capsules or dissolve them in water. Patients requiring mechanical ventilation who cannot swallow capsules can have capsules crushed under water and administered through nasogastric or orogastric tube in collaboration with OSU pharmacy as outlined in Appendix B. Each dose of study drug should be taken at approximately the same time every day.

Patients may NOT consume grapefruit or grapefruit products, Seville oranges (including marmalade containing Seville oranges), or star fruit during the study.

If a dose is not taken at the scheduled time, it can be taken as soon as possible on the same day with a return to the normal schedule the following day. The subject should not take extra capsules to make up the missed dose. Missed doses will not be made-up. If vomiting occurs no replacement dose is to be given.

If patients are discharged from the hospital prior to completing the course of study drug, the remainder drug to complete two cycles of therapy will be sent home with the patient at discharge and a pill diary will be used.

Medication administration records will be used to determine compliance with study therapy.

7.3. Concomitant Medication Use Guidelines For Study Participants

Warfarin is excluded throughout the trial as is grapefruits and grapefruit juice, starfruit, and Seville oranges. Cancer therapy is also prohibited during the study. Medications allowed with caution are found in Appendices

A. All concomitant medications need to be documented in the electronic medical record.

Standard of Care COVID 19 Therapy

All standard of care therapy for COVID 19 that is not specifically prohibited in the protocol is acceptable and encouraged. Current standards of care can be found in Table 2 of Appendix C. It is acknowledged that standards of care are likely to change during the course of the study. Standard of care therapy should be considered in the context of toxicities expected with ibrutinib, and therapies that are expected to have overlapping toxicities should be used with caution.

Anticoagulants and Anti-platelet agents

Laboratory studies have shown that *in vitro* ibrutinib can prevent platelets from aggregating normally. While serious bleeding has been uncommon in patients treated to date, it is possible that treatment with the study drug could increase the risk of bruising or bleeding, particularly in subjects receiving oral anticoagulants or antiplatelet agents. Besides warfarin, which is prohibited, patients on the study may receive any other anticoagulants or antiplatelet agents at prophylactic or therapeutic doses. Subjects receiving anticoagulants and/or antiplatelet agents in conjunction with ibrutinib should be observed closely for any signs of bleeding or bruising and ibrutinib should be withheld in the event of any significant

bleeding events. Patients receiving both therapeutic anticoagulation and anti-platelet agents should be considered at higher risk for bleeding.

Inhibitors or inducers of CYP3A

As ibrutinib is primarily metabolized by CYP3A. Concomitant use of ibrutinib and drugs that strongly or moderately inhibit CYP3A can increase ibrutinib exposure, these should be avoided as possible. Avoid grapefruit and Seville oranges during ibrutinib treatment as these contain moderate inhibitors of CYP3A. Strong inhibitors of ibrutinib should be avoided during the course of the trial. Dose adjustment of ibrutinib due to concomitant use of CYP3A inhibitors should follow Table 1 below as applicable. See Appendices

A for a summary of cautionary medications.

Table 1: Ibrutinib Dose Modification Guidance for Co-Administration with CYP3A Inhibitors

Ibrutinib for COVID 19

Co-administered Drug	Recommended Ibrutinib Dose for the Duration of the Inhibitor Use ^a	Recommended Ibrutinib Dose for the Duration of the Study IF THE STARTING STUDY DOSE IS 280 mg
Mild CYP3A inhibitors	420 mg once daily. No dose adjustment required.	280 mg daily. No dose adjustment required
Moderate CYP3A inhibitors	280 mg once daily.	140 mg once daily
Voriconazole 200 mg twice daily Posaconazole suspension 100mg once daily, 100 mg twice daily, or 200 mg twice daily	140 mg once daily.	70 mg once daily
Posaconazole at higher doses ^b	70 mg once daily.	Discontinue ibrutinib
Other strong CYP3A inhibitors	Avoid concomitant use and consider alternative with less CYP3A inhibitory potential. If these inhibitors will be used short-term (such as anti-infectives for seven days or less), interrupt ibrutinib. If the benefit outweighs the risk and long-term dosing is required (more than seven days), reduce ibrutinib dose to 140 mg once daily for the duration of the inhibitor use.	Avoid concomitant use and consider alternative with less CYP3A inhibitory potential. If these inhibitors will be used short-term (such as anti-infectives for seven days or less), interrupt ibrutinib. If the benefit outweighs the risk and long-term dosing is required (more than seven days), reduce ibrutinib dose to 140 mg once daily for the duration of the inhibitor use.

a. Monitor for adverse reactions to ibrutinib (IMBRUVICA) and interrupt or modify dose as recommended (see Dosage and Administration).

b. Posaconazole at higher doses (posaconazole suspension 200 mg three times daily or 400 mg twice daily, posaconazole IV injection 300 mg once daily, posaconazole delayed-release tablets 300 mg once daily).

A list of common CYP3A inhibitors and inducers is provided in **Appendix A**. For further information, please refer to the current version of the ibrutinib IB and examples of inhibitors, inducers, and substrates can be found at <http://medicine.iupui.edu/clinpharm/ddis/main-table/>.

Tocilizumab has the potential to reduce ibrutinib concentrations, and thus should be used with caution

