7. TREATMENT PLAN

7.1. Overview and Design of Study

7.1.1 Phase 1b

This study will begin with a 12 patient lead-in cohort to establish safety and better characterize toxicity prior to the randomized component. For safety purposes, patients will be enrolled in cohorts of 3 for the first 6 patients, and patients will receive ibrutinib at a dose of 420 mg daily. Dose limiting toxicity (DLT) will be evaluated during the first 14 days of treatment.

DLT would be considered to be any of the following:

- Grade 4 hematologic toxicity that persists for 3 or more days that is considered at least possibly related to ibrutinib.
- Grade 3 or higher non-hematologic toxicity that are considered at least possibly related to Ibrutinib with the exception of nausea, vomiting, diarrhea, or electrolyte abnormality, unless these persist for at least 3 days despite maximal supportive care
- Any grade 3 or higher fungal or bacterial infection (excluding line infection, catheter-associated UTI, or C difficile infection), cardiac toxicity (with the exception of hypertension) or bleeding regardless of the attribution. We note, though, that many

patients in the hospital that develop infection of any grade will be treated with IV antibiotics, and that per CTCAE criteria, those graded 3 or higher would be those where IV antibiotics are indicated, not only for those where IV are chosen due to convenience.

- Non COVID-19 related neutropenic fever

Further enrollment to this dose level will stop if 2 of the first 3 evaluable patients or if at least 33% of subsequent evaluable patients (i.e, 2/6, 3/9, or 4/12) have DLT. If unacceptable toxicity is observed, Ibrutinib will decrease to 280 mg daily, and another 12 patient lead-in will be evaluated at this lower dose level following the same stopping rules. If toxicity is acceptable, the study will proceed to the randomized component. Patients who do not receive 14 days of Ibrutinib for reasons other than toxicity or DLT will be replaced for the purposes of the safety and tolerability assessment.

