8.2. Dose modification of study drug (Ibrutinib or placebo) for Hepatic Impairment

Patients who develop grade 2 increase in bilirubin or ALT/AST should have study drug dose reduced to 2 capsules (equivalent to 280 mg daily) for either arms. If liver function tests return to grade 1 levels, study drug can be increased to 3 capsules (equivalent to 420 mg daily). Patients who develop grade 3 or higher increase in bilirubin or AST/ALT or who have evidence of hepatic failure should have study drug discontinued permanently.

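### Table 1's 280 mg column ties the reduced dose to the study, not to inhibitor use, so two rows would keep ibrutinib low after the inhibitor stops

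*Combined protocol and SAP*

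**What the plan says.** Section 7.3 makes Table 1 the operative rule: "Dose adjustment of ibrutinib due to concomitant use of CYP3A inhibitors should follow Table 1 below as applicable". The table has two dose columns. The first, whose unadjusted dose is 420 mg, is headed "Recommended Ibrutinib Dose for the Duration of the Inhibitor Use". The second is headed "Recommended Ibrutinib Dose for the Duration of the Study IF THE STARTING STUDY DOSE IS 280 mg".

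The second column comes into play only through the lead-in rule in Section 7.1.1: "If unacceptable toxicity is observed, Ibrutinib will decrease to 280 mg daily". Study treatment lasts 14 days (Section 7.6).

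The row for other strong inhibitors has the same text in both columns. It ends its longer-term option with "reduce ibrutinib dose to 140 mg once daily for the duration of the inhibitor use".

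**The concern.** The heading of the 280 mg column disagrees with the parallel column and with its own last row. Where a cell gives a dose and no duration, the heading is the only statement of how long that dose lasts. Read as written, it keeps the patient on the reduced dose for the rest of treatment, even after the interaction that prompted the reduction has gone.

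The protocol does not supply the missing rule elsewhere. Sections 7.6, 8.1 and 8.2 do not say when a CYP3A-related reduction ends. Section 8.2 does state a return-to-dose rule for liver tests ("If liver function tests return to grade 1 levels, study drug can be increased to 3 capsules"), so the plan gives such a rule where one is wanted.

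At stake is the dose that ibrutinib patients receive, in a 280 mg lead-in or later in Arm A. They would get less drug than the 420 mg column's rule implies, with no stated reason. The replacement rule in Section 7.1.1 covers patients who do not complete 14 days of drug for reasons other than toxicity. It does not mention patients held at a lower dose, so such a patient could still count towards the assessment of 280 mg.

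**Working it through.** **Step 1: which rows the heading governs (280 mg column of Table 1).**

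| Inhibitor | Cell in the 280 mg column | Does the heading change anything? |
|---|---|---|
| Mild | "280 mg daily. No dose adjustment required" | No, the dose is not reduced |
| Moderate | "140 mg once daily" | Yes, no duration in the cell |
| Voriconazole, lower-dose posaconazole | 70 mg daily | Yes, no duration in the cell |
| Higher-dose posaconazole | Stop ibrutinib | No, the cell itself stops the drug |
| Other strong | Interrupt, or 140 mg during inhibitor use | No, the cell carries its own limit |

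Two rows are affected.

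**Step 2: size of the effect.** The plan gives no figure to reproduce, so this is an illustration.

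Inputs from the plan: a starting dose of 280 mg, 14 treatment days, and a reduced dose d of 140 mg or 70 mg. Assumptions: the inhibitor starts on day s = 1, 4 or 8 and runs for L = 3, 5 or 7 days. "For the study" is taken to mean through day 14.

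- Total under the heading: (s − 1) × 280 + (15 − s) × d
- Total under inhibitor use: L × d + (14 − L) × 280
- Days kept low after the inhibitor stops: 15 − s − L

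Example with d = 70, s = 1, L = 3. Heading: 14 × 70 = 980 mg. Inhibitor use: 3 × 70 + 11 × 280 = 3,290 mg. The shortfall is (3,290 − 980) / 3,290 = 70.2%, with 15 − 1 − 3 = 11 days kept low.

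Moderate inhibitor (d = 140). Totals under inhibitor use are 3,500, 3,220 and 2,940 mg for L = 3, 5 and 7.

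| Start day | Heading total (mg) | Shortfall, L = 3 / 5 / 7 |
|---|---|---|
| 1 | 1,960 | 44% / 39% / 33% |
| 4 | 2,380 | 32% / 26% / 19% |
| 8 | 2,940 | 16% / 9% / 0% |

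Voriconazole or lower-dose posaconazole (d = 70). Totals under inhibitor use are 3,290, 2,870 and 2,450 mg.

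| Start day | Heading total (mg) | Shortfall, L = 3 / 5 / 7 |
|---|---|---|
| 1 | 980 | 70% / 66% / 60% |
| 4 | 1,610 | 51% / 44% / 34% |
| 8 | 2,450 | 26% / 15% / 0% |

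Days kept low after the inhibitor stops, for both rows and L = 3 / 5 / 7: 11 / 9 / 7 from day 1, 8 / 6 / 4 from day 4, and 4 / 2 / 0 from day 8. The gap is zero whenever the inhibitor runs to day 14.

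**The case against.** The best defence is that context settles the reading. The table's title and the sentence that sends staff to it both concern co-administration, so once the inhibitor stops the table arguably no longer applies. Read literally, the heading cannot describe a dosing period, because the study runs until 12 months after the last enrolment (Section 7.9) while drug is given for 14 days. This supports calling the heading a slip. It does not remove the conflict: staff dosing from a table go by its column headings, and this one states a different duration from its neighbour.

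The opposite defence is that the longer reduction is deliberate. The column applies only after 420 mg has proved too toxic, and it is already stricter for higher-dose posaconazole, where 70 mg becomes a stop. That is possible, but no sentence says so, and the column's own last row points the other way. The fix leaves room for a stated clinical reason.

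Two limits on size stand. Section 7.3 asks staff to avoid strong and moderate inhibitors where possible, and chronic strong-inhibitor use is an exclusion, so few patients may be affected. Also, the only capsule strength described is 140 mg (Sections 7.2 and 10.1.1), so the 70 mg totals show what the cell instructs and not necessarily what could be dispensed.

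**Conclusion.** The point holds and is minor. The heading contradicts the parallel column and its own last row, and in two rows it prescribes a reduced dose after the reason for it has ended. In the illustration the shortfall in total dose runs from 0% to 44% in the moderate row and from 0% to 70% in the 70 mg row, depending on the assumed start day and course length.

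It arises only if the trial moves to a 280 mg start, a patient takes one of these inhibitors, the course ends before day 14, and staff follow the heading. The plan gives no basis for estimating how often that would happen. The intention-to-treat comparison, the type I error and the sample size do not depend on it.

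**What to change.** Reword the heading of the second dose column to "Recommended Ibrutinib Dose for the Duration of the Inhibitor Use", followed by the existing condition that the starting dose is 280 mg. If the sponsor's clinicians do intend a reduction for the rest of treatment, they should say so, give the reason, and reconcile the row for other strong inhibitors with it. No dose in the table needs to change for this point, nor does the instruction to stop ibrutinib with higher-dose posaconazole. The cost is an edit to one table heading, with no effect on sample size, visits or analysis.

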5. PATIENT SELECTION

5.1. Inclusion Criteria

1. Hospitalization for confirmed PCR positive COVID-19 infection
2. Active cancer, defined as a solid malignancy either undergoing active therapy, receiving therapy within 1 year, or a hematologic malignancy under active therapy or observation.
3. Age ≥ 18
4. Patients with evidence of pulmonary involvement who meet any of the followings; presence of infiltrates on chest X-ray or CT scan or need for supplemental oxygen $< 8\text{L}$ nasal cannula or pulse oximetry $< 94\%$ on room air.
5. Biochemical values within the following limits:
 - a. Creatinine clearance $\geq 25 \text{ ml/min}$ by Cockcroft-Gault equation

- b. Total bilirubin $\leq 1.5 \times$ upper limit of normal (ULN) unless bilirubin rise is due to Gilbert's syndrome or of non-hepatic origin
- c. Alanine aminotransferase (ALT) and aspartate aminotransferase (AST) $\leq 3 \times$ ULN
- 6. Hematology values must be within the following limits (no need to hold growth factors or transfusions):
 - a. Absolute neutrophil count (ANC) $\geq 1000/\text{mm}^3$ independent of growth factor support
 - b. Platelets $\geq 50,000/\text{mm}^3$
- 7. Ability to swallow capsules or receive opened capsule content via nasogastric or enteral feeding tube as described in 7.2
- 8. Ability to provide informed consent indicating that they understand the purpose of and procedures required for the study, including biomarkers, and are willing to participate in the study. If a patient is unable to provide informed consent (e.g. does not possess decisional capacity), a legally authorized representative may provide consent for the patient.
- 9. Women of childbearing potential and men who are sexually active must be practicing a highly effective method of birth control during and after the study consistent with local regulations regarding the use of birth control methods for subjects participating in clinical trials. Men must agree to not donate sperm during and after the study. For females, these restrictions apply for 1 month after the last dose of study drug. For males, these restrictions apply for 3 months after the last dose of study drug.
- 10. Women of childbearing potential must have a negative serum (beta-human chorionic gonadotropin [β -hCG]) or urine pregnancy test at Screening. Women who are pregnant or breastfeeding are ineligible for this study.

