10.1.1. Formulation and Storage

Ibrutinib and placebo will be supplied as capsules. Capsules are provided as a hard gelatin capsule containing 140mg of ibrutinib or placebo.

Bottles should be stored at room temperature 20°C to 25°C (68°F to 77°F) with excursions permitted between 15°C and 30°C (59°F to 86°F).

The investigational pharmacy at OSU will dispense a 14 day supply of capsules on day 1. This supply will be used to administer daily doses while the patient is admitted. If a patient is discharged before the completion of the 14 days of therapy, the remaining supply will be sent home with the patient along with a pill diary.

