10.1.2. Administration

The study drug will be administered in the form of 3 capsules orally once daily (either placebo or ibrutinib). The Ibrutinib arm will receive 420mg (3 X 140-mg capsules) orally once daily. The capsules are to be taken around the same time each day with 8 ounces (approximately 240 mL) of water. The capsules should be swallowed intact and patients should not attempt to open capsules or dissolve them in water. Patients requiring mechanical ventilation who cannot swallow pills can have capsules opened and administered through nasogastric or orogastric tube in collaboration with OSU pharmacy. In this case, please see preparation worksheet (Appendix B). Each dose of study drug should be taken at approximately the same time every day.

Patients may NOT consume grapefruit or grapefruit products, Seville oranges (including marmalade containing Seville oranges), or star fruit during ibrutinib treatment.

If a dose is not taken at the scheduled time, it can be taken as soon as possible on the same day with a return to the normal schedule the following day. The subject should not take extra capsules to make up the missed doses. If vomiting occurs no replacement dose is to be given.

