10.1.3. Overdosage

Any dose of study drug administered in excess of that specified in this protocol is considered to be an overdose. Signs and symptoms of an overdose that meet any SAE criterion must be reported as a SAE in the appropriate time frame and documented as clinical sequelae to an overdose, and would lead to unblinding.

There is no specific experience in the management of ibrutinib overdose in patients. No maximum tolerated dose (MTD) was reached in the Phase 1 study in which subjects received up to 12.5 mg/kg/day (1400 mg/day). Healthy subjects were exposed up to single dose of 1680 mg. One healthy subject experienced reversible Grade 4 hepatic enzyme increases (AST

and ALT) after a dose of 1680 mg. Subjects who ingested more than the recommended dosage should be closely monitored and given appropriate supportive treatment.

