Appendix A: INHIBITORS AND INDUCERS OF CYP3A

NOTE: Itraconazole and ketoconazole can be replaced with voriconazole for study subjects.

Inhibitors of CYP3A	Inducers of CYP3A
Strong inhibitors:	
indinavir	carbamaze
nefnavir	nevirapine
ritonavir	barbiturates
clarithromycin	glucocorticoids
Itraconazole	modafinil
Ketoconazole	oxcarbazepine
nefazodone	pioglitazone
saquinavir	troglitazone
suboxone	pioglitazone
telithromycin	Strong CYP3A inducers
cobicistat	avasimibe
boceprevir	carbamazepine
mibefradil	phenobarbital
telaprevir	phenytoin
troleandomycin	rifabutine
posaconazole	rifampin
voriconazole	St. John's Wort
Moderate inhibitors:	
aprepitant	
amprenavir	
amiodarone	
atazanavir	
ciprofloxacin	
isavuconazole	
crizotinib	
darunavir	
dronedarone	
erythromycin	
diltiazem	
fluconazole	
fosamprenavir	
grapefruit juice	
Seville orange juice	
verapamil	
imatinib	
Weak inhibitors:	
cimetidine	
fluvoxamine	
All other inhibitors:	
chloramphenicol	
delavirdine	
gestodene	
mifepristone	
norfloxacin	
star fruit	

Appendix B: Preparation Worksheet for NG or OG Tube Administration of Ibrutinib**PREPARATION WORKSHEET FOR IBRUTINIB**Preparation Worksheet for Ibrutinib for each dose that is prepared.**IP Preparation Steps for Ibrutinib 140 mg****Preparation Date:** dd/ mmm/ yyyy**Subject No.** _____ HH: mm**Preparation area:****PREPARATION OF THE DRUG PRODUCT**

INSTRUCTIONS	RECORD	
1. Confirm the preparation area is clean and cleaning is performed according to site procedure.	  /   Performed by _____ Date _____	
2. Ensure the dispensing labels are prepared		
3. Remove 3 capsules from the bottle.	Medication Kit Number: _____	
4. Record the time the capsules are removed from the bottle.	dd / mmm / yyyy HH: mm	
5. Open the 3 capsules and place their contents into a glass beaker. Tap the capsule bodies and caps against the side of the beaker to remove any excess material remaining within the capsule bodies and caps.		
6. Prepare a glass beaker filled with 30 mL of water, add to the beaker with the capsule contents, and swirl/mix until the contents are uniform.	Volume of water in beaker (mL): _____	
7. Allow the dispersion to stand for at least 15 minutes.	Standing Start: HH: mm	
8. Affix an 18 gauge needle to a 60 mL syringe, briefly swirl the beaker, and draw the dispersed capsule contents into the syringe.	Standing End: HH: mm	

Ibrutinib for COVID 19

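### Two cells of Table 1 call for 70 mg once daily, which a patient swallowing the supplied 140 mg capsules cannot be given

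*Combined protocol and SAP*

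**What the plan says.** Section 7.3 makes Table 1 the dosing rule: "Dose adjustment of ibrutinib due to concomitant use of CYP3A inhibitors should follow Table 1 below as applicable". The table has one column for the 420 mg start and one for the 280 mg start. The dose "70 mg once daily" appears twice:

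- in the 420 mg column, for posaconazole at higher doses;
- in the 280 mg column, for voriconazole 200 mg twice daily or posaconazole suspension at lower doses. This column applies only if the safety lead-in de-escalates.

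For higher-dose posaconazole at the 280 mg start, the table says "Discontinue ibrutinib".

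On supply, Section 10.1.1 states: "Capsules are provided as a hard gelatin capsule containing 140mg of ibrutinib or placebo". No other strength, liquid form or alternate-day schedule is described. On administration, Section 10.1.2 states: "The capsules should be swallowed intact and patients should not attempt to open capsules or dissolve them in water". Section 7.2 agrees and also rules out crushing.

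The exception is tube dosing. Inclusion criterion 7 (Section 5.1) requires: "Ability to swallow capsules or receive opened capsule content via nasogastric or enteral feeding tube as described in 7.2". Sections 7.2 and 10.1.2 describe this route for ventilated patients who cannot swallow. The Appendix B worksheet instructs: "Open the 3 capsules and place their contents into a glass beaker".

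**The concern.** A dosing table that staff are told to follow should contain only doses that can be made from the supplied product. These two cells do not, and they apply when a strong CYP3A inhibitor is expected to raise ibrutinib exposure.

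The protocol does not tell staff to round up, and it gives no other default for these cells. Staff must improvise. If one capsule were given, Section 10.1.3 would classify it: "Any dose of study drug administered in excess of that specified in this protocol is considered to be an overdose". Under that section, overdose signs or symptoms that meet a serious adverse event criterion lead to unblinding, and Section 8.3 takes unblinded patients off study drug.

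The cells can be reached. Section 5.2 excludes chronic strong-inhibitor treatment and active uncontrolled fungal infection, but a patient could start an azole on study. Appendix A allows voriconazole to replace itraconazole or ketoconazole, and fungal infection is counted in a secondary endpoint (Section 3.2).

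**Working it through.** **Inputs.** Capsule strength 140 mg (Section 10.1.1); full dose 3 capsules (Section 10.1.2); doses from Table 1 (Section 7.3) and Table 2 (Section 8.1); 12 lead-in patients and 66 randomized 1:1, with a maximum sample size of 120 after re-estimation (Section 13).

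**The plan's own figure.** 3 × 140 = 420 mg, as Section 10.1.2 states.

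**Test.** When capsules are swallowed whole, dose ÷ 140 must be a whole number.

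| Table 1 row | 420 mg start | Capsules | 280 mg start | Capsules |
|---|---|---|---|---|
| Mild inhibitor | 420 mg | 3 | 280 mg | 2 |
| Moderate inhibitor | 280 mg | 2 | 140 mg | 1 |
| Voriconazole or lower-dose posaconazole | 140 mg | 1 | **70 mg** | **0.5** |
| Higher-dose posaconazole | **70 mg** | **0.5** | stop | none |
| Other strong inhibitor, more than 7 days | 140 mg | 1 | 140 mg | 1 |

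Table 2 uses 420, 280 and 140 mg, which are 3, 2 and 1 capsules. Only the two 70 mg cells fail the test.

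**If one capsule were given instead.**

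- Ratio to the stated dose: 140/70 = 2.
- 420 mg start: intended reduction 420/70 = 6-fold; delivered 420/140 = 3-fold.
- 280 mg start: intended reduction 280/70 = 4-fold; delivered 280/140 = 2-fold.

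**Tube dosing.** The worksheet yields 3 × 140 = 420 mg only. A dispersed capsule could in principle be split, so here 70 mg is a missing preparation step rather than an impossibility.

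**Patients who could be overexposed.** The documents give no rate of posaconazole or voriconazole use. I assume 1% to 5% of patients fall in an affected cell.

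- Planned size: 12 + 66/2 = 45 on active drug; 1% is 0.45 and 5% is 2.25.
- Maximum size: 12 + 120/2 = 72; 1% is 0.72 and 5% is 3.6.
- Maximum size plus a second 12-patient lead-in at 280 mg: 72 + 12 = 84; 1% is 0.84 and 5% is 4.2.

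Each patient would be affected for at most the 14 treatment days.

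**The case against.** The mismatch itself is not in dispute. The case against giving it weight has five parts.

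- **The table accepts 140 mg with a strong inhibitor elsewhere.** For other strong inhibitors needed for more than seven days, where benefit outweighs risk, it recommends one capsule at either starting dose. This stands. The 2-fold ratio compares nominal doses, and the documents give no exposure or toxicity figure to attach to it. Harm from one capsule is not shown; departure from the stated dose is.
- **Staff can already stop the drug.** Strong inhibitors are to be avoided, the table is headed as guidance, and Section 7.6 lets the treating physician end treatment. This is true, and it reduces the gap to a missing default. It does not make 70 mg deliverable.
- **The two cells are never both live at one starting dose.** This is correct. On the planned 420 mg course only the higher-dose posaconazole cell applies.
- **The three-capsule worksheet affects every reduced dose given by tube, not just 70 mg.** This is also correct, and tube dosing goes through the pharmacy. The main point rests on patients who swallow capsules.
- **Holding the drug would be stricter than the row for other strong inhibitors.** It would, but the table already has that ordering: 70 mg or a stop for the named azoles against 140 mg for the others.

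**Conclusion.** The concern holds as a minor operational error. Two of Table 1's dose instructions cannot be followed with the only product described, for any patient swallowing capsules. That rests on the text and on 70/140 = 0.5, with no assumption needed.

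The reach is small: about 0 to 2 active-drug patients at the planned size, and about 1 to 4 at the maximum size with a second lead-in. Both ranges rest on the assumed 1% to 5% rate. The consequence of giving one capsule is conditional, because nothing in the protocol directs it. The randomization, primary endpoint, sample size, power and type I error are unchanged.

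**What to change.** In both cells, replace the 70 mg dose with an instruction to hold study drug while the inhibitor is used, or to discontinue it. The table already has wording of both kinds: a stop for higher-dose posaconazole at the 280 mg start, and an interruption for short-term use of other strong inhibitors. In the randomized part, apply the rule to study drug in both arms so that the blind is kept.

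Keep 70 mg only if matching 70 mg active and placebo capsules are supplied, or if a half-dose preparation is written down for the patients concerned.

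**Cost.** Two cells of wording. Affected patients lose up to 14 days of study drug, which are not recovered because Section 7.2 does not allow missed doses to be made up. On the same assumed rate, at the planned size of 12 + 66 = 78 patients, this is 0.78 to 3.9, or about 1 to 4 patients. At the maximum with a second lead-in, 12 + 12 + 120 = 144, it is 1.44 to 7.2, or about 1 to 7. The 70 mg supply or half-dose route avoids that loss and preserves the table's intended dose, but adds a supply item or a pharmacy procedure.
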